#### *4.12.3 Pharmacokinetic Analysis for Ethnic Difference*

The PK parameters for total Mo ( $C_{\text{max}}$ ,  $\text{AUC}_t$ , and  $\text{AUC}_{\infty}$ ) will be evaluated for Japanese and non-Japanese cohorts, using an analysis of variance (ANOVA) statistical model [1,2] with cohort and period as the fixed effects, and subject as a random effect, using the natural logarithms of the data. The within-subject CV for the  $C_{\text{max}}$ ,  $\text{AUC}_t$ , and  $\text{AUC}_{\infty}$  will be estimated using the mean squared error from the ANOVA. The mean between-group differences and their 90% and 95% CIs are back-transformed to the linear scale and represent estimates of ratios of geometric means.

In addition, the Japanese versus non-Japanese cohorts will be evaluated using descriptive statistics: for each cohort, the geometric means and the associated 95% confidence intervals of  $C_{\text{max}_n}$ ,  $\text{AUC}_{t_n}$ , and  $\text{AUC}_{\infty_n}$  will be reported at each dose.

### **4.13 Exploratory Analyses**

#### *4.13.1 Dose Proportionality*

Dose proportionality for each cohort and cohorts combined will be assessed graphically and using power models [1,2]. The log (PK parameters) is included as

a response variable and log (dose) is included as a fixed effect in the power model. The following PK parameters will be assessed for dose proportionality: dose-normalized  $C_{max}$  ( $C_{max\_n}$ ), dose-normalized  $AUC_t$  ( $AUC_{t\_n}$ ), dose-normalized  $AUC_{\infty}$  ( $AUC_{\infty\_n}$ ). The ratio of geometric means will be estimated with its 2-sided 90% and 95% confidence intervals.

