#### **Intervention Groups and Duration:**

[figure not shown]
Each subject will receive a total of 2 doses of ALXN1840 (1 single oral dose of 15 mg and 1 single oral dose of 60 mg) according to the study drug dosing regimen outlined above.

The planned study duration is approximately 56 days; up to 27 days for screening and approximately 29 days for dosing and follow-up.

**Data Monitoring Committee:** There will not be a Data Monitoring Committee, but provision is included for a Safety Review Committee, if needed.

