## 9.4.3.1.3. Exploratory Analyses

Dose-proportionality of ALXN1840 PK between the 15 mg and 60 mg doses within each cohort and with combined cohort data will be assessed via graphical display and evaluated quantitatively via dose-normalized  $C_{\text{max}}$  and AUC values.

Relationships between CL/F and body size (body weight [kg] and BMI [kg/m²]) will be evaluated graphically for the Japanese and non-Japanese cohorts and with combined cohort data. If suggested by the graphs, regression models may be fit to the data.

Detailed exploratory analyses will be described in the PK/PD DAP finalized before database lock.

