### **4.12 Pharmacokinetic Data Analysis Plan**

All plasma concentration data will be listed for each individual subject and summarized at each time point by cohort and period. Individual and mean concentrations versus nominal time on linear and semi-log scales will be presented graphically by period.

The PK population will be used to present the summary of PK parameters.

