#### *4.12.2 Pharmacokinetic Parameters*

Individual plasma concentration data for ALXN1840, assessed as plasma total Mo concentration-time data, with actual sampling dates and times calculated relative to the actual date and time for the start of dose administration in each Dosing Period, will be used to derive the PK parameters. PK parameters will be calculated

using non-compartmental analyses with Phoenix® WinNonlin® Version 8.0 or higher. If missing actual sampling dates and times, then the nominal time relative to the start time of the administration will be used.

The following plasma total Mo PK parameters will be derived for each subject and period:

- **Cmax [ng/mL]:** Maximum observed plasma concentration
  - o For multiple peaks, the highest post-dose concentration will be reported as Cmax
- **Cmax\_n[ng/mL]/[mg]:** Dose normalized maximum observed plasma concentration
  - o Calculated as Cmax /dose
- **Tmax [h]:** Time to maximum observed plasma concentration
  - o In case that multiple peaks are available of equal magnitude at the highest post-dose concentration, the earliest Tmax will be reported
- **AUCt [h\* ng/mL]:** Area under the plasma concentration versus time curve from time zero (dosing) to the last quantifiable concentration
- **AUCt\_n [h\* ng/mL]/[mg]:** Dose normalized area under the plasma concentration versus time curve from time zero (dosing) to the last quantifiable concentration
  - o Calculated as AUCt /dose
- **AUC∞ [h\* ng/mL]:** Area under the plasma concentration versus time curve from time zero (dosing) extrapolated to infinity
- **AUCextr (%):** The percentage of AUC∞ extrapolated.
  - o Subjects with an AUCextrap > 20% will be flagged, and parameters that are dependent on AUC∞ will also be flagged (AUC∞, **AUC∞\_n**, CL/F, Vd/F and Frel).
- **AUC∞\_n [h\* ng/mL]/[mg]:** dose normalized area under the plasma concentration versus time curve from time zero (dosing) extrapolated to infinity
  - o Calculated as AUC∞ /dose
- **λz [1/h]:** Apparent terminal-phase elimination rate constant
  - o Only those data points that are judged to describe the terminal log-linear decline will be used in the regression

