  - o A minimum number of 3 data points in the terminal phase will be used in calculating λz, with the line of regression starting at any post-Cmax data point (Cmax should not be part of the regression slope)
- **t1/2 [h]:** Terminal elimination half-life
  - o Calculated as ln(2)/ λz
- **CL/F [L/h]:** Apparent total clearance

- Calculated as  $\text{dose}/\text{AUC}_{\infty}$
- **$V_d/F$  [L]:** Apparent volume of distribution during terminal phase
  - Calculated as  $\text{dose}/(\lambda_z * \text{AUC}_{\infty})$
- **$F_{\text{rel}}$ :** Relative bioavailability defined as the ratio of the geometric means for the dose normalized  $\text{AUC}_{\infty}$  parameter for the ALXN1840 Japanese cohort over the ALXN1840 non-Japanese cohort by dose strength of 15 mg or 60 mg.

PK parameters will be listed for each individual subject and summarized by cohort and period. Descriptive statistics for PK parameters will include number of observations (n), arithmetic mean (Mean), standard deviation (SD), arithmetic coefficient of variation (%CV), geometric mean, geometric %CV, median, minimum and maximum.

For the relative bioavailability, a 95% CI for the ratio of the geometric means will be provided. To calculate CIs of geometric mean ratios, dose normalized  $\text{AUC}_{\infty}$  will be log-transformed and CIs will be constructed for the mean difference of log-transformed parameters, assuming that log-transformed parameters are normally distributed. The CIs are then back-transformed to receive CIs for the geometric mean ratios. The geometric mean ratios and their 95% CIs will be tabulated.

Some PK parameters may not be calculated for all or some subjects if the concentration data are not deemed to be amenable to evaluation. Explanations for PK parameters that could not be estimated will be provided in the CSR. Subjects who vomit post-dose will have their plasma concentration profile evaluated for inclusion in the PK analysis.

Analyses of other PK data including, but not limited to those, of PUF Mo may be conducted.

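### The dose-proportionality power model in SAP 4.13.1 names no subject effect although each subject is planned to receive both doses; fitted with log(dose) alone, its confidence intervals ignore the pairing

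*SAP*

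**What the plan says.** SAP 4.13.1 plans power models for each cohort and for the cohorts combined. The log PK parameter is "a response variable and log (dose) is included as a fixed effect in the power model". The parameters are the dose-normalised Cmax, AUCt and AUC∞. For output, "The ratio of geometric means will be estimated with its 2-sided 90% and 95% confidence intervals". No subject, cohort or period term is named.

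The design is paired. Under Intervention Groups and Duration in the protocol synopsis, "Each subject will receive a total of 2 doses of ALXN1840": 15 mg in Dosing Period 1 and 60 mg in Dosing Period 2. SAP 4.12.2 follows this: "The following plasma total Mo PK parameters will be derived for each subject and period".

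The section just before, SAP 4.12.3, models the same kind of repeated data for the ethnic comparison with cohort and period fixed and "subject as a random effect".

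Protocol 9.4.3.1.3 describes only graphs and dose-normalised values, and then says: "Detailed exploratory analyses will be described in the PK/PD DAP finalized before database lock". SAP 4.12 is itself headed "Pharmacokinetic Data Analysis Plan", so it is unclear whether that DAP is a separate document.

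**The concern.** A programmer who fits only the stated term regresses 2n log values on log(dose) as if they came from 2n different people. Stable differences between subjects then stay in the error term, although they cancel when each subject's 60 mg value is compared with his or her own 15 mg value.

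At stake is the precision of a stated exploratory objective. Protocol 2.2 reports no clear dose-proportionality in the Phase 2 study and suggests small numbers and high inter-subject variability as possible reasons. Protocol 4.2 says the present design was chosen to control variability within and between subjects. A model without a subject effect gives up that advantage, and wider intervals around 1 make real non-proportionality harder to see.

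**Working it through.** **Inputs.** Log-scale SD 0.35 (SAP 3.3, CV of 35% used as the SD). Completers: 10 per cohort, 20 combined (SAP 3). The documents give no within-subject CV or correlation, so the correlation rho between a subject's two log values is an assumption, taken over a range. Pairs are taken as complete and the log SD as equal at both doses.

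**The plan's own figure.** For the between-cohort comparison, t(0.95, 18 df) × 0.35 × √(2/10) = 1.734 × 0.35 × 0.447 = 0.271, and exp(±0.271) = 0.76 to 1.31. This matches SAP 3.3. No precision figure is given for dose proportionality.

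**Formulas.** With two dose levels, the power-model slope times ln 4 equals the difference in log means, so the 90% half-widths on the log scale are:
- log(dose) only: t(0.95, 2n−2) × SD × √(2/n)
- with a subject effect: t(0.95, n−1) × SD × √(2(1−rho)/n)

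Their ratio is [t(0.95, 2n−2)/t(0.95, n−1)]/√(1−rho), which does not depend on the SD.

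**Break-even correlation.** Setting the ratio to 1:
- n=10: 1 − (1.734/1.833)² = 0.105
- n=20: 1 − (1.686/1.729)² = 0.049

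For 95% CIs the values are 0.137 and 0.065. Below break-even the paired interval is slightly wider because it has fewer degrees of freedom: 0.287 against 0.271 at rho = 0, n=10.

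**Size over assumed correlations, 90% CI, SD 0.35.**

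| rho | n=10: log(dose) only | n=10: with subject | times as wide | n=20: log(dose) only | n=20: with subject | times as wide |
|---|---|---|---|---|---|---|
| 0.25 | 0.271 | 0.248 | 1.09 | 0.187 | 0.166 | 1.13 |
| 0.5 | 0.271 | 0.203 | 1.34 | 0.187 | 0.135 | 1.38 |
| 0.75 | 0.271 | 0.143 | 1.89 | 0.187 | 0.096 | 1.95 |

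For a true ratio of 1 at n=10 and rho 0.5, this is 0.82 to 1.22 instead of 0.76 to 1.31. In 100,000 simulated trials per setting at n=10, the nominal 90% CI without a subject effect covered the truth in 93.9%, 97.3% and 99.6% of trials at rho 0.25, 0.5 and 0.75.

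**A scenario from protocol Table 4 (60 mg, Study WTX101-102).** Assume that the variation seen with uncoated capsule plus PPI, fasted, is stable between-subject variation, and that the rest of the fasted EC-tablet variation is within-subject. Log SD = √(ln(1+CV²)) throughout; within-subject variance is the EC variance minus the capsule variance; rho is capsule variance over EC variance.

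| Parameter | EC CV (log SD) | Capsule + PPI CV (log SD) | Within SD | rho | n=10, 90%: log(dose) only / with subject | times as wide |
|---|---|---|---|---|---|---|
| AUC∞ | 5955/17258 = 34.5% (0.335) | 4022/21047 = 19.1% (0.189) | 0.277 | 0.32 | 0.260 / 0.227 | 1.15 |
| AUCt | 5635/16026 = 35.2% (0.341) | 3509/19809 = 17.7% (0.176) | 0.293 | 0.27 | 0.265 / 0.240 | 1.10 |
| Cmax | 98.0/376 = 26.1% (0.256) | 69.6/442 = 15.7% (0.157) | 0.203 | 0.37 | 0.199 / 0.166 | 1.19 |

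At n=20 the factors are 1.18, 1.14 and 1.23. Within this scenario they are upper figures, because the capsule CV already contains some within-subject variation. The scenario also borrows across formulations and covers 60 mg only.

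**The case against.** The best reply is that an omission is not a model. SAP 4.13.1 says that log(dose) is included as a fixed effect; it does not say that nothing else is. Calling it a fixed effect is mixed-model language, and the section cites the same two references as the random-subject ANOVA in 4.12.3. Those references are not available here, and the protocol leaves detail to a DAP. All of this stands. A reader might infer that the SAP prescribes an unpaired analysis, and the documents do not support that. They support only that the term is not stated in any text provided.

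The paired contrast is also already inside the 4.12.3 model. Period 1 is always 15 mg and Period 2 always 60 mg, so period and dose are the same factor there. That model's period contrast on the log scale, minus ln 4, is the within-subject dose-normalised 60/15 comparison for the combined cohorts. This stands in part: the SAP does not plan to report that contrast, and it yields no per-cohort intervals. Under SAP 4.12.2, "PK parameters will be listed for each individual subject and summarized by cohort and period", so paired ratios could be worked out afterwards, but the planned CIs would not use them.

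A reader might also infer a larger effect. Assuming a within-subject CV of 20% against a total CV of 35%, both converted to log SDs, the n=10 interval is 0.264/0.162 = 1.62 times as wide. Nothing in the documents supports 20% over, say, 30%, where the factor is 0.264/0.241 = 1.10.

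Finally, the analysis is exploratory, has no acceptance limits, and errs on the conservative side. That is correct, and it sets the priority.

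**Conclusion.** The point holds as a conditional one of minor weight. SAP 4.13.1 states no subject effect for data that are paired by design. If the model is fitted with only the stated term, the 90% and 95% CIs for the 60/15 mg ratio ignore the pairing. Above the break-even correlation they are too wide; how much too wide depends on a correlation the documents do not give. In the Table 4 scenario the excess is 10 to 19% at n=10, and it approaches a doubling only at a correlation near 0.75.

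Three stronger inferences are not supported. The intervals would not be too narrow: positive correlation gives over-coverage. The point estimate would not be biased by the omission when pairs are complete. It could differ between the two models if pairs are incomplete, which can happen because the PK population in SAP 4.2 admits subjects with AUC from one period. And the primary cohort comparison is untouched, since 4.12.3 already has subject as a random effect.

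**What to change.** Add one sentence to SAP 4.13.1: the power model includes subject as a random effect, in the per-cohort fits and in the combined fit. Report the 60/15 ratio of dose-normalised geometric means with its 90% and 95% CIs from that model, with 1 as the reference for proportionality. If a separate PK/PD DAP exists, it should say the same.

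The cost is that sentence and one RANDOM statement in the SAS program. No new data are needed, and no other planned analysis changes.

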#### 3.1 Overall Design

The study has a screening phase (Days -28 to -2), 2 Dosing Periods (Day -1 to Day 11 each), and an end-of-study (EOS) visit.

After completing the screening phase, enrolled subjects will be admitted to an inpatient facility (CRU) on Day -1 for dosing on Day 1 in Dosing Period 1.

Subjects will be then be readmitted to the CRU for Dosing Period 2 dosing, at least 14 days following the 15 mg dose.

Subjects are confined to the CRU from Days 1 to Day 11 for both Dosing Periods and have samples obtained for PK/PD assessments as well as safety evaluations performed (as detailed in Tables 1 and 2 of the trial protocol). Subjects are discharged 10 days after dosing with Period 1 and Period 2 following the 240 hour post dose procedures, unless medically necessary to extend their confinement.

The subjects in each cohort will follow the dosing regimen as follows:

[figure not shown]
Dosing Period	Planned dose
Dosing Period 1	Subjects will receive a single dose of one 15 mg ALXN1840 enteric-coated (EC) tablet at Hour 0 on Day 1 of Period 1 following an overnight fast.
Dosing Period 2	Subjects will receive a single dose of 4 × 15 mg (for a total of 60 mg) ALXN1840 EC tablets at Hour 0 on Day 1 of Period 2 following an overnight fast.

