#### *4.12.1 Values Below the Limit of Quantification and Missing Values*

If a Below the Limit of Quantification (BLQ) value occurs in a profile before the first measurable concentration, it will be assigned a value of zero concentration. If a BLQ value occurs after a measurable concentration in a profile and is followed by a value above the lower limit of quantification, then the BLQ value will be omitted following visual inspection of the plasma concentration versus time profile to assess the appropriateness of this assignment. If a BLQ value occurs at the end of a collection profile (after the last quantifiable concentration), the value will be treated as missing data. If 2 BLQ values occur in succession, the profile will be deemed to have terminated at the first BLQ value and any subsequent concentrations will be omitted from PK calculations following visual inspection of the plasma concentration versus time profile to assess the appropriateness of this assignment.

Samples with no reportable value due to a bioanalytical issue or missing samples will be set to missing, and will not be included in the PK calculations. If a subject vomited following dose administration, then their profile will be examined to determine the impact of this on PK parameter estimation.

When calculating the mean or median value for a concentration at a given time point, all BLQ values will be set to zero except when an individual BLQ falls between 2 quantifiable values, in which case it will be omitted.

For tabulation, graphical representation, and calculation purposes, all samples with no reportable value (or missing samples) observed after dosing will be set to missing.

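### Dose-normalised AUCt (SAP 4.13.1) can overstate the 60/15 mg exposure ratio under linear PK if the 15 mg profile falls below the assay limit before 240 h

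*SAP*

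**What the plan says.** SAP 4.12.2 defines AUCt for each subject and period as "Area under the plasma concentration versus time curve from time zero (dosing) to the last quantifiable concentration", and AUCt_n as AUCt divided by dose. SAP 4.12.1 handles the end of a profile as follows: "If a BLQ value occurs at the end of a collection profile (after the last quantifiable concentration), the value will be treated as missing data". Two successive BLQ values also end a profile. That section mentions a BLQ result that is "followed by a value above the lower limit of quantification", but neither document gives the value of the limit.

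Each subject is dosed twice. In Period 1, "Subjects will receive a single dose of one 15 mg ALXN1840 enteric-coated (EC) tablet"; in Period 2 the dose is 60 mg. Both periods are sampled to 240 h (protocol Table 2).

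SAP 4.13.1 introduces Cmax_n, AUCt_n and AUC∞_n with "The following PK parameters will be assessed for dose proportionality", and adds: "The ratio of geometric means will be estimated with its 2-sided 90% and 95% confidence intervals". Protocol 9.4.3.1.3 likewise says that proportionality is "evaluated quantitatively via dose-normalized" Cmax and AUC values. Neither document defines an AUC over a common interval, says what to do when the two periods end at different times, or says which measure governs if the three disagree. For AUC∞, SAP 4.12.2 flags profiles with more than 20% extrapolated and ties no exclusion rule to the flag.

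**The concern.** With a fourfold dose difference and one assay limit, the lower-dose curve reaches the limit first. If that happens inside the sampling window, the 15 mg AUCt leaves out a larger share of its total exposure than the 60 mg AUCt does. Dividing by dose does not repair this, because the two areas cover different stretches of time. Under linear PK, truncation of this kind can only raise the 60/15 ratio of AUCt_n.

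At stake is the reading of an exploratory objective. Protocol 2.2 reports no clear dose-proportionality in Study WTX101-201, and the present study is meant to support 15 to 60 mg in Japanese patients. An apparent more-than-proportional rise produced by the assay limit would be an unhelpful addition to that record.

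**Working it through.** **The plan's own figure.** No precision is stated for dose proportionality. The only stated precision is for the cohort comparison (protocol 9.2, SAP 3.3). It reproduces: 1.734 × 0.35 × √(2/10) = 0.271, and exp(±0.271) = 0.76 to 1.31. The 35% CV agrees with Table 4 (5,635/16,026 = 35.2%).

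**Inputs.** Protocol Table 4, EC tablet fasted, 60 mg: AUC∞ 17,258 h·ng/mL, AUC(0-t) 16,026 h·ng/mL, λz 0.0149 per h. Last sample at 240 h for both doses. The LLOQ is an assumption, shown over a range.

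**Mono-exponential approximation with exactly linear PK.**
- C0 = λz × AUC∞ = 0.0149 × 17,258 = 257 ng/mL at 60 mg, and 257/4 = 64.3 ng/mL at 15 mg.
- At 240 h, exp(−0.0149 × 240) = 0.028, giving 7.2 ng/mL at 60 mg and 1.8 ng/mL at 15 mg.
- Profile end = the smaller of 240 h and ln(C0/LLOQ)/λz.
- Unmeasured share = exp(−λz × profile end).
- AUCt_n ratio 60/15 = (1 − share at 60 mg)/(1 − share at 15 mg).

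| Assumed LLOQ (ng/mL) | 15 mg ends (h) | 60 mg ends (h) | Unmeasured, 15 mg | Unmeasured, 60 mg | AUCt_n ratio |
|---|---|---|---|---|---|
| 1.8 or below | 240 | 240 | 2.8% | 2.8% | 1.00 |
| 2.5 | 218 | 240 | 3.9% | 2.8% | 1.01 |
| 5 | 171 | 240 | 7.8% | 2.8% | 1.05 |
| 10 | 125 | 218 | 15.6% | 3.9% | 1.14 |
| 15 | 98 | 191 | 23.3% | 5.8% | 1.23 |

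**Gap between the profile ends.** The full gap is ln(4)/0.0149 = 93 h, and it arises only if both curves reach the limit before 240 h, which needs an LLOQ above about 7.2 ng/mL. At 5 ng/mL the schedule caps the 60 mg profile, and the gap is 240 − 171 = 69 h.

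**Check with a biexponential oral profile.** This was fitted approximately to the same Table 4 means (half-life 46.5 or 51 h) and sampled at the protocol times. The ratio was 1.00 at an LLOQ of 1 or below, 1.00 to 1.01 at 2, 1.06 to 1.09 at 5, 1.15 to 1.21 at 10 and 1.24 to 1.34 at 15. The simple approximation therefore does not inflate the effect.

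**The other two measures.** Cmax_n does not depend on where the profile ends. In the biexponential model the AUC∞_n ratio is 1.00 to 1.01 up to an LLOQ of 10, and at most about 1.05 at 15. The extrapolated share at 15 mg rises to about 17 to 21% at 10 and 24 to 28% at 15.

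**Size against a plausible interval.** The documents give no within-subject CV. Assume 15% to 25% and 20 subjects compared within subject. The log-scale 90% half-width is 1.729 × √ln(1 + CV²) × √(2/20), or 0.08 to 0.13. The bias is ln(1.054) = 0.05 at an LLOQ of 5 and ln(1.138) = 0.13 at 10. Only towards the upper figure could truncation alone move the interval off 1.00. SAP 4.13.1 names no subject term, and an unpaired interval would be wider.

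**Common interval.** If both profiles are cut at the same time T, the unmeasured share is exp(−λz × T) for both and the ratio is exactly 1. The sampled model returned 1.000 at LLOQ 5 and 10.

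**The case against.** The strongest reply is that the effect depends on a figure nobody can read from these documents, and that the plan already contains the means to notice it. Sampling to 240 h is about 4.7 half-lives (240/51.0). With an LLOQ near 2 ng/mL or lower, the bias is at most about 1%. Cmax_n and AUC∞_n sit in the same analysis, so a rise in AUCt_n alone would point to truncation. The extrapolated percentage is derived and individual semi-log profiles are plotted. All of this stands, and it keeps the point minor. It does not remove it: AUC∞_n leans most on extrapolation where truncation is worst, and in the mono-exponential model the 20% flag is reached only near 0.20 × 64.3 = 13 ng/mL. The SAP also does not say which AUC measure decides.

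A reader might take the last concentration implied by Table 4, (17,258 − 16,026) × 0.0149 = 18.4 ng/mL, as the assay limit, which would give a ratio of about 1.30. The documents do not support that. In Table 3 the two UC + PPI arms have nearly equal extrapolated shares (1,325/19,862 = 6.7% and 1,067/15,603 = 6.8%) at different exposures, with implied last concentrations of about 18.6 and 15.2 ng/mL. That fits profiles ended by the sampling schedule better than profiles ended by one limit. Table 4 is less clear, so this is not proof either way.

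A reader might also carry the argument over to the cohort comparison. With a true cohort ratio of 1.30 and an LLOQ of 5, the 15 mg ratio becomes 1.30 × (1 − 0.060)/(1 − 0.078) = 1.33 and the 60 mg ratio is unchanged. Pooled over the two doses that is about 1%, against a planned interval of 0.76 to 1.31. It does not call for extra cohort tables.

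**Conclusion.** The concern holds in conditional form, for one of three exploratory measures. If the 15 mg profile becomes unquantifiable before 240 h, the 60/15 ratio of AUCt_n is biased upward under exactly linear PK. On Table 4 values the bias is nil at an LLOQ of about 1.8 ng/mL or below, about 1% at 2.5, about 5% at 5 and about 14% at 10. These figures rest on mean parameters, a mono-exponential curve and an assumed LLOQ; the biexponential check gives similar or slightly larger values.

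A reader might infer that the dose-proportionality analysis is bound to show more-than-proportional exposure. The documents do not support that: without the LLOQ it cannot be said that any truncation will occur, and Cmax_n and AUC∞_n would be little affected or unaffected. The severity is minor, since the objective is exploratory and no acceptance limits are set. The change is still worth making because the direction of the bias is known and the correction is nearly free.

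**What to change.** - **SAP 4.12.2:** for each subject with both periods evaluable, derive a partial AUC from time 0 to the earlier of the two periods' last quantifiable times, and its dose-normalised value.
- **SAP 4.13.1:** add this dose-normalised partial AUC beside AUCt_n. State that the AUC conclusion on dose proportionality rests on it and on AUC∞_n, with AUCt_n supportive only.
- AUCt stays as a listed endpoint, and the cohort analysis in SAP 4.12.3 is unchanged. No fixed-time AUC is needed for the cohort comparison.

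The cost is one partial-AUC setting in WinNonlin and one extra table row, with no new samples. The small downside is that some quantifiable late 60 mg area goes unused in this one measure.
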